### Critical points of laparoscopic surgery

Various points were discussed which are blamed to be responsible for the poor performance of laparoscopy. The current data are briefly summarized focusing on three points:

*Tumor hygiene* – One of the main criticisms of the LACC study concerns the lack of standardization of the surgical procedure. Uterine manipulators were used routinely. By manipulation of the cervix, a tumor cell spread into the abdominal cavity can be assumed. In a proof-of-principle study, we were able to show the simple way of contamination by means of indocyanine green spillage. The study results by Köhler et al. indicate the importance of the so-called tumor hygiene. As early as 2016, Kong et al. described an increased number of recurrences in cases where intracorporal colpotomy (laparoscopic) was performed, compared to those where this occurred vaginally (16.3% vs. 5.1%, p=0.057). In an updated analysis, these authors were again able to show that intracorporal colpotomy is an independent predictive factor for reduced disease-free survival. The multivariate analysis showed an HR of 3.1 (95% CI 1.2–7.9), which roughly corresponds to the difference between the abdominal and laparoscopic arm of the LACC study. Interestingly, patients who received a vaginal colpotomy in the cited studies of Köhler (4.5 year 95.8%) and Kong (2 years 98%) also showed very high disease-free survival rates, although a possible selection bias cannot be excluded in these studies.

*The learning curve* – Especially in the case of technically complex procedures, it seems logical that the experience and technical skills of the surgeon influence the success of the operation. It is critical to question whether this point has been adequately taken into account in the LACC study and in the various register studies, especially in the context of the widespread introduction of laparoscopic surgery within a very short period of time. Interestingly, Cusimano et al. in their analysis of Ontario registry data could not confirm an effect of the learning curve. The analysis by the

American Cancer Registry showed no difference in disease-free survival depending on the volume of surgery either. The data from Eoh et al., which indicated a clear effect of the learning curve in the robot-assisted approach, are interesting. There was a significantly lower survival rate in patients who underwent surgery between 2006 and 2013 compared to those treated between 2013 and 2018, who in turn had no survival disadvantage compared to patients who underwent abdominal surgery. To an even greater extent, Matsuo et al. analyzed survival after laparoscopic radical hysterectomy depending on the operational volume of the hospitals, in a retrospective Japanese registry study. After propensity score matching there was an impressively reduced likelihood of recurrence if the patients underwent surgery in an experienced clinic instead of an inexperienced clinic (HR 0.69, 95% CI 0.57–0.84). The data are supported by the register data from Sweden and Denmark and the study by Köhler et al., as they report all the results of highly specialized centers. A German population-based cohort study including 413 patients with early stage IA1-IIB2 showed that minimally invasive surgery was associated with improved RFS and OS compared with the open surgery. However, after adjustment for treatment center, the surgical approach was not associated anymore with significant difference in RFS (HR = 0.61, 95% CI 0.31–1.19; p = 0.143).

Probably not only the learning curve seems to be decisive for success, but also the content of this learning curve and the surgical technique ultimately applied. Important results of a retrospective international multicenter study were published by Chiva et al., which showed a disease-free survival at 4.5 years of 79% for laparoscopy and 89% for the abdominal approach. This work demonstrated that the outcomes of laparoscopic surgery were better when no uterine manipulator was used (4.5 years DFS 83% vs. 73%) or a vaginal cuff closure was performed (4.5 years DFS 93% vs. 74%).

*Robotic surgery* – A major criticism of the LACC study by robotic surgeons is the low proportion of robot-assisted radical hysterectomies (16%). It is argued that the more accurate preparation by robot-assisted surgery leads to better survival rates. This effect could not be demonstrated in the LACC study. On the other hand, the Swedish and Danish registry studies, which evaluated only robot-assisted surgery, have not been able to demonstrate a difference to the abdominal procedure in their large analyses. An analysis by Brandt et al. also showed similar results regarding survival in 196 patients at Memorial Sloan-Kettering Cancer Center and pointed out the benefits in terms of a lower complication rate of this surgical procedure. The retrospective character and the possible selection bias are emphasized as a criticism of these studies. It should also be noted that, in the Scandinavian countries in particular, there is a very strong centralization of a few highly specialized clinics, so that the effects of the learning curve will probably have to be taken into account. The large American registry study of Melamed et al. showed reduced disease-free survival for robotic-assisted radical hysterectomy compared to the abdominal procedure (HR 1.61; 95% CI 1.18– 2.21).

Recently, a meta-analysis of observational studies by Nitecki et al. found that minimally invasive radical hysterectomy was associated with an elevated risk of recurrence and death compared with open surgery. This meta-analysis of 15 observational studies revealed a 71% higher hazard of recurrence and death in the minimally invasive radical hysterectomy group compared to the open surgery cohort. As a strength of their meta-analysis the authors described their various methods used to minimize confounding, e.g. by demographic factors, tumor stage or size. Unfortunately, the authors did not evaluate the association of different surgical techniques with survival after laparoscopic radical hysterectomy.

Therefore, we performed a systematic review and meta-analysis where we not only compared the survival rates of open hysterectomy and laparoscopic hysterectomy, but also the results of risk groups including uterine manipulators and prophylactic vaginal suture. 30 studies fulfilled the inclusion criteria. Five prospective, randomized-control trials were included. Patients were analyzed concerning the surgical approach (open surgery AH, laparoscopic surgery LH).

Additionally, three subgroups were created for the LH group: high risk group (manipulator), intermediate risk group (no manipulator, intracorporal colpotomy) and low risk group (no manipulator, vaginal colpotomy). Regarding OS, the meta-analysis showed a superiority of AH (0.96 [0.93; 0.97]) over the whole LH group. Interestingly, OS was significantly higher in LH low risk (0.96 [0.94; 0.98]) compared to LH intermediate risk group (0.93 [0.91; 0.94]). OS rates were comparable in AH and LH low risk group. DFS was higher in the AH group compared to the LH group in general (0.92 [0.88; 0.95] vs. 0.87 [0.82; 0.91]), whereas the application of protective measures (no uterine manipulator in combination with vaginal colpotomy) was associated with increased DFS in laparoscopy (0.91 [0.91; 0.95]). In conclusion, DFS and OS in laparoscopy appear to be depending on surgical technique. Protective operating techniques result in improved minimal invasive survival and seem to be equivalent to open hysterectomy.

### **Ongoing studies**

Further surgical studies are urgently needed to provide greater clarity on this issue, in particular with the exclusion of manipulators and laparoscopic colpotomy. Especially experienced laparoscopic surgeons want to incorporate their own experiences and data into the joint therapy decision. However, retrospective data should carefully be interpreted and potential selection bias should always be considered. The results of the LACC study cannot be discounted without comparable other randomized trials. On the contrary, the results of the LACC study must always remind everyone of the importance of good scientific work. Surgical medicine should also seek randomized-controlled trials. Specialized surgical procedures should be carried out by experts and should be subject to meticulous quality control.

Under Swedish leadership, the RACC study has already been launched, which compares the robot-assisted with the abdominal-open radical hysterectomy, similar to the LACC study. The Chinese LACC trial plans to randomly assign 1448 patients in 28 centers in China to undergo MIS (robot-assisted or laparoscopic RH) or abdominal RH with the requirement of experienced surgeons. Strict guidelines for preventive maneuvers and possible tumor hygiene are not implemented. Therefore, we see a need for a multicenter study comparing the laparoscopic approach with the requirements under which the procedure was developed earlier with the abdominal procedure. This includes measures that prevent peritoneal contamination with tumor. The Trial of Robotic Versus Open Hysterectomy Surgery in Cervix Cancer (ROCC/GOG-3403) in the US has a similar design, in which only the transcervical manipulators are prohibited and specific surgical techniques for "tumor containment" are necessary (ClinicalTrials.gov Identifier: NCT04831580).

## 1.5 Study Rationale

Laparoscopic, minimally invasive surgery has become standard treatment for several benign and malignant diseases including endometrial or colorectal cancer because of reduced bleeding, less complication rates, shorter hospital stays and lower costs while achieving same oncological safety. After publication of the LACC study, multiple gynecologic oncologists abandoned LRH from their clinical routine. Others criticize study methodology and surgical techniques which were not standardized and suggest strategies to improve outcomes after LRH. Important results of recently published retrospective national and international studies by Köhler, Chiva and Kong et al. demonstrated that the outcomes of laparoscopic surgery were comparable to open surgery when no uterine manipulator, vaginal colpotomy and vaginal cuff closure were performed. Although patient and tumor characteristics are not completely comparable between those different studies, these results raise the strong hypothesis that outcomes of laparoscopic radical hysterectomy depend on surgical technique and the possibility of tumor cell spread into the intraperitoneal cavity. The updated German S3 guideline emphasizes these very good oncological results of preventive operative measures which underline the hypothesis of necessary surgical tumor hygiene and recommend the validation by randomized studies. Therefore, only a well-designed, well-powered and stringently conducted study with expert

centers can finally answer the question whether LRH is an oncological equivalent and less invasive alternative to ARH in early stage cervical cancer.

The idea of minimal invasive surgery is that patients gain significant profit from decreased morbidity, less pain, shorter hospital stays and faster recovery. Therefore, potential adjuvant therapies like radiation or chemotherapy can be administered directly after the primary treatment due to decreased risks for perioperative complications such as wound healing disorders. Furthermore, the reduced lower socioeconomic burden of laparoscopy is linked to indirect costs with earlier return to work and increased work productivity. The main aim of the G-LACC trial is to prove that laparoscopic hysterectomy is non-inferior to abdominal hysterectomy with regard to safety and disease-free survival. Thus, the G-LACC trial will have significant clinical impact on the future surgical approach for early cervical cancer.

### **1.6** Risk Benefit Evaluation

The large randomized LACC study demonstrated that MIS is associated with a higher rate of recurrence and death from disease which was confirmed by a recent meta-analysis of observational studies. This is deeply concerning since no clear cause has been established. Most industrialized countries had abandoned the open approach in favor of MIS because of its general advantages with decreased morbidity, less pain, shorter hospital stays and faster recovery. Furthermore, substantial investments in research, education and equipment were triggered in the field of laparoscopic oncologic surgery which led to impressive developments such as fluorescent-guided sentinel techniques. Our sophisticated meta-analysis showed that oncologic outcome in laparoscopy appear to be depending on surgical technique. Protective operating techniques resulted in improved minimal invasive survival and were equivalent to open hysterectomy.

At the moment, a significant number of centers returned back to open surgery, however, others don't. Since MIS is a standard approach in gynecologic surgery, the results of this trial will have a major impact upon national/international guidelines and therefore, on daily clinical practice. The use of nation-wide clinical tumor and quality registers should further improve the oncologic management and constitute a reliable data source for research and quality improvements. The preliminary analyses from the German cancer centers support an advantage of MIS over open surgery, however, this should be interpreted with caution due to its retrospective nature.

Since the LACC trial demonstrated an association between MIS and disease recurrence, the risk for similar outcomes in the G-LACC trial cannot be neglected. However, the potential risk should be balanced against the potential benefits of MIS including less complications, improved quality of life, and future developments within the laparoscopic platforms.

A Data Monitoring Committee (DMC) will be implemented for close supervision of the accruing information, to detect possible harms and to assure continuous risk/benefit assessment. The DMC will review the data in the context of safety, validity and quality on a regular basis and may recommend early termination of the trial in case the DMC observes a significant difference between both treatment groups (see section 7.3 and 9.2).

### 2 STUDY DESIGN AND OBJECTIVES

### 2.1 Study Design

The G-LACC trial is a prospective, interventional, multicenter, open-label, randomized and controlled non-inferiority operative trial.

Eligible patients will be randomly allocated to both treatment arms in a 1:1 ratio. Within an accrual period of 4 years, 378 patients will be included per arm (756 in total) across all sites. The Follow-up period after surgery will take a minimum of 5 years.

[figure not shown]

Figure 1: Study scheme of the G-LACC trial

In the standard arm, radical hysterectomy is performed as per standard technique (abdominal radical hysterectomy (Piver type 2 or 3 or Querleu & Morrow Type B or C) with salpingectomy +/- oophorectomy. Ovaries may be removed or preserved +/- transposition. Surgery includes pelvic lymph node dissection or optional sentinel lymph node biopsy (SNB) according to current guidelines in both arms.

In the experimental arm, radical hysterectomy is performed as per standard conventional 2D/3D laparoscopic or robotic assisted technique (Querleu & Morrow Type B or C) with salpingectomy +/- oophorectomy. Ovaries may be removed or preserved +/- transposition. The following protective measures are mandatory for the minimal-invasive arm: LEEP/conization before randomization or closure of the vagina before colpotomy. Transcervical manipulators are not permitted. Use of uterus manipulators/ cervical adapter (without transcervical device) are allowed only after LEEP/conization. Meticulous dissection of pelvic (sentinel) lymph nodes including use of endobags and avoiding the dissemination of cancer cells will be implemented (tumor hygiene).

Due to the positive results of the SHAPE trial presented at ASCO 2023, in both arms simple hysterectomy can be considered for patients with low-risk early-stage cervical cancer (SHAPE-criteria: tumor < 2 cm, < 10 mm depth of stromal invasion (LEEP/cone) BUT has to be determined BEFORE randomization. Simple hysterectomy has to be performed as extrafascial hysterectomy and the preparation of a max. 5mm vaginal cuff is required to ensure negative margins. Surgery can be performed including removal of the sentinel lymph nodes following the concept of sentinel lymph node biopsy (SNB) and according to the current guidelines.

# 2.2 Study Objectives

The primary objective is to investigate the oncologic safety of laparoscopic or robot-assisted radical /simple hysterectomy compared to abdominal radical/simple hysterectomy using pre-specified surgical techniques and qualitative standards and to demonstrate the non-inferiority with a non-inferiority margin of 2.3 for the hazard ratio for disease free survival (DFS), defined as the time from randomization to disease recurrence or death from any cause (whichever occurs first).

The secondary objective is to evaluate overall survival, disease recurrence, quality of life, complications and treatmentassociated morbidity, treatment costs and cost effectiveness.

## 2.3 Study Endpoints

### 2.3.1 Primary Endpoint

### Disease-free survival

Disease-free survival (DFS) is defined as the time from randomization to disease recurrence or death from any cause (whichever occurs first). The date of disease recurrence is defined as the date of biopsy.

### 2.3.2 Secondary Endpoints

### Overall survival

Overall survival (OS) is defined as the time from randomization to death from any cause.

### Disease recurrence

Local/pelvic recurrence is defined as occurrence of vaginal or pelvic side-wall (including nodal recurrence) recurrence while the occurrence of extra-pelvic lymph nodes, port site metastases, parenchymatous organ, carcinomatosis, bone metastases are defined as distant recurrence at 3 and 4,5 years. A suspicion of disease recurrence (clinical or by imaging) should be verified by histopathological assessment. The date of recurrence of disease is defined as the date of biopsy. Disease recurrence will be assessed and recorded at each follow-up visit starting with 6 months post-surgery (visit 5).

### Quality of life including lymphatic side effects

Health Related Quality of Life (HRQoL) will be assessed by using validated questionnaires comprising EORTC QLQ-30, EORTC QLQ-CX24 EuroQoL EQ-5D-3L. Sexual activity will be assessed by using the Sexual Activity Questionaire (SAQ). Additionally, lymphatic side effects will be assessed by the investigator using CTCAE 3.0 and by the patient using the LYMQOL questionnaire. HRQoL and lymphatic side effect assessments will be conducted over the whole course of the trial (see sections 5.3.11 and 5.3.12 and Appendix 0 and 12.2).

### Complications and treatment-associated morbidity

Intra- and post-operative treatment-related complications are recorded. In addition, other serious adverse events (SAEs) are captured at each visit starting with surgery (section 6).

### Health care costs

Treatment costs and cost effectiveness will be determined as incremental cost-effectiveness ratios. Direct costs will be assessed via internal accounting and billing systems within the hospitals. The quality-adjusted life years (QALYs) gained with the intervention will be calculated based on health status measures for trial participants, with valuations of changes in health status and quality of life based on the EQ-5D questionnaire. QALY calculations will then be used for a cost-utility analysis.

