# 5.2.4 Follow Up Visits

The Follow Up period begins with visit 4 (1 month after surgery +/- 7 days) and lasts for at least 5 years. Completed assessments will be collected either in connection to the visit at the clinic, electronically (eCRF) or per conventional mail.

The following evaluations are performed during the Follow-up period:

- Length of stay (visit 4)
- Recording of post-operative complications (visits 4–6)
- Recording of pathology of the uterus (visit 4) \*
- Record of adjuvant treatment (if applicable, visit 6)
- Quality of life questionnaire (visits 4–10)
- Lymphatic side effects questionnaire (visits 4–8)
- Record of recurrence (if applicable, visits 5–10)
- Adverse events (visits 4–8)

\* Tumor size assessment in case of prior LEEP/cone excision should be estimated according to the College of American Pathologists (CAP). In providing the final tumor dimensions, the measurements in any prior specimens, for example LEEP/cone excision, will need to be taken into account. Although it may overestimate the maximum horizontal extent, it is recommended to add together the maximum lateral measurements in different specimens when calculating the final horizontal extent. For a detailed description of the assessments, please see section 5.3.

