## 5.3.6 Length of stay

Please record the number of days spent in hospital.

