## 5.3.12 Quality of Life Assessments

In order to compare the grade of short- and long-term effects on the patients' HRQoL between both treatments (ARH und LRH) all participants will be asked to complete QoL questionnaires at different times over the course of the trial. The QoL assessments' focus will be on late side-effects such as bladder dysfunction, sexual activity, physical-, emotional, and role functioning as well as fatigue and pain.

Patients will complete HRQoL questionnaires in an appropriate language either as electronical patient reported outcome measures or during the clinic visits (by manually filling in hardcopy forms, by accessible computer (eCRF) or by mail). Study personnel, e.g. investigator or study nurses, will not have access to the QoL-forms while answered by the patient in order to avoid any influence.

Eligible patients will be informed orally and in writing about the HRQoL assessment before inclusion in the trial. Baseline assessment will be performed before randomisation to one of both treatment arms at visit 1 but only after written and oral informed consent is obtained. Post-surgery assessments will be conducted 1 and 6 months as well as 1, 2, 3, 4 and 5 years after treatment at visits 4 to 10 (see section 5.1). Completed questionnaires will be collected either in connection to the visit at the clinic, electronically via eCRF or per conventional mail and are always considered as source documents.

The following questionnaires will be completed by all patients included in the G-LACC trial as stated above (see Appendix 0):

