#### **5.3.14** Record if recurrence

In addition to the follow-up visits as scheduled in the study calendar (see section 5.1), patients will receive followup care according to national guidelines. Follow-up care includes physical examination and medical consultation among other optional procedures (e.g. tumor marker or cytology). In case of abnormal findings during follow-up or clinical suspicion of disease recurrence, imaging diagnostic should be performed. Recurrence of disease must be verified by histopathological assessment. The date of biopsy counts as the date of recurrence. State where the recurrence occurred:

- Type of analysis (CT, MRT, Biopsy, other)
- pelvic recurrences (vaginal vault, parametrium, pelvic lymph nodes, or other)
- extra pelvic recurrences (abdomen, para-aortic lymph nodes, supraclavicular lymph nodes, or other)
- if possible, an additional blood sample should be collected

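### Hospital accounting is the only cost source described, QALYs run to year 5, and recurrence care outside the trial hospitals is not recorded, so the cost of an arm with more relapses may be understated (secondary endpoint).

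*Protocol*

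**What the plan says.** All references are to the protocol.

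- **Outcome (2.3.2, Health care costs).** "Treatment costs and cost effectiveness will be determined as incremental cost-effectiveness ratios". A cost-utility analysis is to follow. Cost effectiveness is a secondary objective (2.2).
- **Cost source (same paragraph).** "Direct costs will be assessed via internal accounting and billing systems within the hospitals". No other source is named, and neither a start nor an end of cost collection is set.
- **Effects.** QALYs rest on "valuations of changes in health status and quality of life based on the EQ-5D questionnaire". The EQ-5D is completed at baseline and then (5.3.12): "Post-surgery assessments will be conducted 1 and 6 months as well as 1, 2, 3, 4 and 5 years after treatment".
- **Index stay (5.3.6, visit 4).** "Please record the number of days spent in hospital".
- **Adjuvant treatment (5.3.10, visit 6).** Recorded once, by modality, as yes/no items.
- **Recurrence (5.3.14, visits 5 to 10).** The form asks for the type of analysis and then: "State where the recurrence occurred". It has no item for treatment or place of care.
- **Hospital admissions.** Hospitalization makes an event an SAE (6.1). SAEs are collected to one year (5.3.15 and the calendar in 5.1). The list in 5.2.4 runs adverse events to visit 8, which conflicts with this. None of these places describes an item for days in hospital.

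**The concern.** An incremental cost-effectiveness ratio needs costs and effects that cover the same patients, care and period. Here the effect of a relapse in, say, year 3 is measured wherever the patient is treated, because she fills in the EQ-5D herself. The cost of that relapse is counted only if the treatment passes through the books of a trial hospital.

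Care elsewhere is plausible on the protocol's own text. Patients may come from a referral hospital (5.2.1). Follow-up care follows national guidelines with no provider named (5.3.14). Questionnaires may be returned electronically or by mail (5.3.12).

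The gap would not be neutral between arms if one arm relapses more, and that is the possibility the trial exists to examine. It is also a gap in data collection. An analysis plan can choose a perspective or a discount rate, but it cannot easily recover treatment that was never recorded.

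**Working it through.** **Step 1. The plan's own figures (7.2).** Inputs: 94% DFS at 4.5 years, margin HR 2.3, one-sided 2.5%, power 80%, 1:1 allocation.

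- Hazard, open arm: -ln(0.94)/4.5 = 0.01375 per year (stated: 0.0138).
- Events: 4 × (1.960 + 0.842)² / (ln 2.3)² = 45.26 (stated: 45).
- Patients: 45.26/0.06 = 754.3, hence 378 per arm and 756 in total, as stated.

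The event model reproduces and can be used below. The protocol gives no figure for the cost endpoint itself.

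**Step 2. Excess events.** With proportional hazards, the excess at 4.5 years is 0.94 - 0.94^HR.

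- HR 1.0: 0
- HR 1.5: 0.94 - 0.9114 = 0.0286
- HR 2.3: 0.94 - 0.8673 = 0.0727, or 7.3 points

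**Step 3. Uncounted cost per minimally invasive patient.** This is excess × share of recurrence care outside trial hospitals × cost per recurrence. The documents give neither a unit cost nor a share. Assumed: EUR 20,000-60,000 per recurrence; shares of 0, 25% and 100%; every DFS event counted as a recurrence.

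| HR | 0% elsewhere | 25% elsewhere | 100% elsewhere |
|---|---|---|---|
| 1.0 | 0 | 0 | 0 |
| 1.5 | 0 | EUR 140-430 | EUR 570-1,720 |
| 2.3 | 0 | EUR 360-1,090 | EUR 1,450-4,360 |

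Example, HR 2.3 at 100%: 0.0727 × 20,000 ≈ 1,450 and 0.0727 × 60,000 ≈ 4,360. A quarter of these gives about 360 and 1,090.

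Over the full 5 years of the EQ-5D the excess at HR 2.3 is (1 - e^(-0.01375×2.3×5)) - (1 - e^(-0.01375×5)) = 0.0798. That gives 0.0798 × 20,000 ≈ 1,600 to 0.0798 × 60,000 ≈ 4,790 at 100%, so the horizon changes little.

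**Step 4. How much the one-year SAE window could cover.** Under the plan's exponential model, the share of 5-year events that falls in year 1 is (1 - e^(-0.01375))/(1 - e^(-0.06875)) = 0.0137/0.0664 = 0.21. At HR 2.3 it is 0.0311/0.1463 = 0.21. About four in five relapses would therefore come after the SAE window has closed.

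**The case against.** **Recurrence treatment is partly counted.** A reader might infer that it is left out altogether. The text does not support that. Section 2.3.2 sets no end date and does not limit costs to the index stay, so treatment at a trial hospital is in that hospital's billing system. Exclusion criterion 8 also removes patients who live too far away for adequate follow-up, so treating all care as being elsewhere is a poor default. This stands, and it is why the 100% column is a ceiling.

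**The direction of the final result is open.** A reader might infer that the cost-effectiveness result favours whichever arm relapses more. It need not. Relapse and death also lower that arm's QALYs. Only the cost side is shifted.

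**Resource use is not a blank.** A reader might infer that no visit records readmissions. Admissions that qualify as SAEs are recorded in year 1, adjuvant treatment is recorded by modality, and the surgical form records operation time and transfusions. The gap is narrower: recurrence treatment, later admissions, days, and care elsewhere.

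**Indirect costs.** The rationale (1.5) says that laparoscopy's lower burden is "linked to indirect costs with earlier return to work and increased work productivity", and nothing on work is collected. But 2.3.2 promises direct costs only and no objective mentions work. A direct-cost view is a legitimate choice, so this is no defect.

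**A separate plan may add sources.** Perspective, horizon and unit costs may be set in an analysis plan or health-economic plan that is not at hand. That is fair for those choices. It does not answer the missing data items, which belong in section 5.

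**Conclusion.** The point holds as a cheap improvement to one secondary endpoint. To the extent that recurrence care is given outside the trial hospitals, the cost of the arm with more relapses is understated in the incremental cost-effectiveness ratio.

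At the non-inferiority margin the understatement is about EUR 360-1,090 per minimally invasive patient with a quarter of the care elsewhere, and at most EUR 1,450-4,360. It is zero if DFS is equal in the two arms, which is the planning assumption, or if all care is at trial hospitals.

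The direction follows from the text. The size rests on an assumed unit cost, an assumed share of care elsewhere, and on counting every DFS event as a treated recurrence. The last assumption overstates it, because DFS includes death from any cause. The documents do not support saying that recurrence care is uncounted, or that the overall result must favour the arm that relapses more. The DFS comparison and the sample size are not touched.

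**What to change.** 1. In 2.3.2, state that costs cover the same 5-year horizon as the QALYs.
2. At the existing follow-up visits, record recurrence treatment by modality and days of hospital admission, wherever the care was given. Add the items to 5.1, 5.2.4 and 5.3.14.
3. Value care given elsewhere with one unit-cost set per country. Keep hospital accounting for care at the trial hospitals, with a rule that the same care is not counted twice.

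No new visit is needed, and adjuvant treatment is already recorded by modality. The cost is a few eCRF items, a little more data entry at sites and a protocol amendment. It should be made early, because care given elsewhere is hard to reconstruct years later across 20-30 sites.
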